both demonstrate the characteristic waveform, VEP amplitudes are significantly smaller in iASD for both P_{60} - N_{75} ($p=.005$) and N_{75} - P_{100} ($p=.009$; Fig.3). Moreover, results from frequency domain analyses indicate that children with iASD showed significantly weaker activity in the 30-36 Hz range ($p<.01$) and 38-48 Hz range ($p=.034$), corresponding to gamma band activity. **Cognitive ability has no effect on the results.** In PMS, we see distinct VEP waveforms with smaller P_{60} - N_{75} amplitudes reflecting deficits in glutamatergic activity (Fig. 2B & 3). All PMS participants displayed reduced excitatory responses (absence of P_{60} - N_{75}), compared to both TD and iASD (p 's $<.001$). Across groups, reduced P_{60} - N_{75} amplitude corresponded to greater sensory hyporesponsiveness on the SAND ($n=32$, $r=-.529$, $p=.001$) and SSP ($n=32$, $r=.403$, $p=.022$), suggesting VEP response marks variability in clinical symptoms. P_{60} - N_{75} amplitude also correlated with *SHANK3* deletion size ($\rho = .414$; Fig.3 inlay) where there was significantly reduced amplitude in patients with larger deletions as compared to point mutations in

[figure not shown]

Figure 3. PMS shows significantly smaller VEP amplitudes relative to TD and iASD. Inset: P_{60} - N_{75} amplitude is further reduced with increased size of *SHANK3* deletion.

SHANK3 ($p=.03$). Yet, all patients with PMS display the expected GABAergic positive peak at P_{100} , indicating a specific, dissociable, glutamatergic VEP signature. These results are consistent with work in animal (Bozdagi et al., 2010) and human neuronal (Shcheglovitov et al., 2013) model systems demonstrating the deleterious effects of *SHANK3* deficiency on glutamatergic system function. In an effort to examine the use of VEPs as a stratification biomarker to aid personalized medicine approaches among an otherwise heterogeneous group of children with iASD ($n=27$), our results suggest that approximately 30% display P_{60} - N_{75} amplitudes within one standard deviation of the PMS mean (Fig.4; purple iASD circles below red dotted line), reflecting “PMS-like” excitatory

deficits.

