glutamatergic dysfunction in PMS and that approximately 50% of children with iASD display deficits in the glutamatergic $P_{60-N_{75}}$ VEP response (Fig.4) akin to those seen in PMS. Given that VEP amplitude is associated with sensory symptoms and that IGF-1 improves clinical symptoms of PMS (Kolevzon et al., 2014), **we hypothesize that $P_{60-N_{75}}$ VEP can be used as a stratification biomarker to predict which individuals with iASD have alterations in neural pathways overlapping with PMS and are therefore likely to respond to rhGH, a treatment that stimulates the release of IGF-1, and consequently, glutamatergic pathways.** Data from ongoing clinical trials at our center provide preliminary support for the use of transient VEPs as a biomarker of target engagement and treatment response. We piloted VEPs in a subset of patients in the context of our IGF-1 clinical trial in PMS. Results from frequency-domain analyses using MSC statistics indicated that IGF-1 consistently increased low gamma power (Fig.5) as measured by change in the band which includes frequencies from 30-36 Hz. There was a significant increase in low gamma MSC following IGF-1 relative to baseline ($n=6$; $p=.048$); when data were inspected individually for consistency of directional trends, MSC increased in 5 of 6 patients (Fig. 5). Increase in high frequency responses from baseline reflects stronger, more consistent excitatory contributions of the VEP, confirming glutamatergic pathway enhancement as a result of treatment, and *suggesting that MSC in the low gamma range represents an ideal biomarker for target engagement and treatment response for rhGH in a 12-week trial.*

Critically, we also saw clinical improvement in sensory hyporeactivity on the SAND with IGF-1 in the same six patients ($p=.037$; Fig.6), which itself is significantly correlated with VEP response. Given that a greater number of visual hyporeactivity symptoms is significantly correlated with smaller $P_{60-N_{75}}$ ($r=-.561$, $p=.024$), in combination with our results showing treatment response on both measures, VEPs and the SAND may represent robust electrophysiological and behavioral measures for evaluating effects of rhGH.

Significance of the Expected Research Contribution.

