of iASD with constrained heterogeneity based on a biological marker. Fourth, given our strong preliminary data in PMS and iASD and existing infrastructure and pipeline for conducting clinical trials, we will test the feasibility and robustness of electrophysiological markers in the context of treatment with rhGH, a step which has yet to be taken successfully in the ASD literature. Fifth, we expect to predict a subset of iASD with high potential to respond to treatment with rhGH based on biological profiles related to PMS, making progress toward a more personalized medicine approach for ASD.

Approach

Aim 3: Evaluate the feasibility of electrophysiological markers as a measure of treatment response.

Introduction. The objective of this aim is to administer rhGH to participants with PMS and iASD to evaluate the feasibility of select electrophysiological biomarkers to: 1) detect change in neural response (engagement) and 2) predict treatment responders on clinical assessments (efficacy). We will also explore the relationship between rhGH dose, IGF-1 level, and electrophysiological response. Participants will be selected based on electrophysiological profiles with reduced $P_{60}-N_{75}$ VEP amplitudes, reflecting impaired glutamatergic function. **Approach:** We will employ a randomized, placebo-controlled, double-blind, crossover design with a four-week wash-out period between phases. **Rationale:** Successful completion of this aim will establish feasibility of select biomarkers for detecting treatment response and advance knowledge about developing targeted treatments for PMS and related subsets of iASD with impaired glutamatergic activity. We expect, based on preliminary data, that the knowledge gained will provide evidence of targeted brain engagement with rhGH, a mechanistic pathway, and evidence of clinical efficacy.

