Research Design. The proposed intervention will recruit 15 children with PMS and 15 children with iASD (2-12 years old). Treatment will follow a randomized, placebo-controlled, crossover format with 12 weeks in each treatment phase (rhGH and placebo). This duration was selected based on evidence with IGF-1 in PMS suggesting our clinical outcomes will be sensitive to change within this time frame (Kolevzon et al., 2014). The primary electrophysiological outcomes will be VEP gamma band activity as our preliminary data with PMS in IGF1 suggests it is sensitive to drug effects (Fig. 5). The primary clinical outcome will be the SAND because: a) our preliminary studies suggest improvement on this measure following IGF-1 (Fig. 6), b) it accurately reflects a sensory phenotype characteristic of PMS and is relevant to a substantial subset of iASD, c) it is associated with electrophysiological measures, and d) it has been validated in ASD and ID.

Inclusion criteria: All participants with PMS will have pathogenic *SHANK3* deletions or sequence variants confirmed in clinical genetics laboratories approved by the Clinical Laboratory Improvement Amendments (CLIA). Genotyping will also be used to confirm the absence of known pathogenic copy number variants in the iASD group. Participants with iASD will meet gold standard diagnostic criteria for ASD, confirmed by the Autism Diagnostic Observation Schedule – 2nd Edition (ADOS-2; Lord et al., 2012) and the Autism Diagnostic Interview-Revised (ADI-R; Lord et al., 1994). All iASD subjects will have a reduced neural response defined by $P_{60}-N_{75}$ amplitudes within one standard deviation of the PMS mean. Subjects will be on stable medication and psychosocial treatment regimens for at least three months prior to enrollment.

Exclusion criteria: 1) closed epiphyses; 2) active or suspected neoplasia; 3) intracranial hypertension; 4) hepatic insufficiency; 5) renal insufficiency; 6) cardiomegaly/valvulopathy; 7) allergy to growth hormone or any component of the formulation; 8) comorbid conditions which prevent participation; 8) visual problems which preclude use of VEP.

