Outcome measures: The primary electrophysiological outcome will be VEP gamma band activity as measured by MSC, which includes frequencies between 30-36 Hz. The secondary electrophysiological outcome will be VEP P₆₀-N₇₅ amplitude. VEP stimuli, data preprocessing, and variable extraction. The primary stimulus condition will be a contrast-reversing checkerboard (100% contrast) of one-minute duration to elicit a transient VEP. VEPs will be analyzed in both time and frequency domains. Waveforms will be standardized into z-scores, segmented to evoking stimuli, filtered 1-100Hz with a 60Hz notch, and averaged across epochs. For time-domain analyses, VEP amplitudes over occipital cortex (Oz) will be measured peak-to-trough (P₆₀-N₇₅, N₇₅-P₁₀₀) and latency (P₆₀, N₇₅, P₁₀₀) will be measured by time-to-peak. Frequency-domain analyses will be conducted using MSC statistics (Zemon et al., 2009, Siper et al. 2016) to quantitatively assess the integrity of overall responses in different frequency bands. MSC reflects response reliability by providing an estimate of signal power relative to the combined power of signal+noise. As such, MSC measures consistency from one trial to the next at a given frequency. A pure signal produces a value of 1 and no signal produces a value of approximately 0.1 (bias level for pure noise); thus, higher MSC values reflect stronger and more consistent oscillatory activity in a given frequency band. Six distinct frequency mechanisms for the tVEP waveform include: Band 1, 6-10 Hz, Band 2, 12-28 Hz, Band 3, 30-36 Hz, Band 4, 38-48 Hz, Band 5, 50-64 Hz (60 Hz electrical noise omitted), Band 6, 66-84 Hz (Siper et al., 2016; Zemon et al, 2009, Zemon & Gordon, in prep.). These MSC frequency bands meet criteria for reliable components regardless of sample size as demonstrated by Monte Carlo computer simulations (Guadagnoli & Velicer, 1988; Stevens, 1996). Based on preliminary data, we expect both P₆₀-N₇₅ amplitude and MSC values in bands encompassing gamma wave activity (Bands 3 and 4) to be decreased in PMS relative to iASD.

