Data Analysis. Following the procedures of a 2x2 cross-over design, each subject is randomized to one of two treatment sequences. First we will use graphical and numerical statistics to characterize treatment-, period- and cross-over effects (Jones & Kenward, 1989). Under the assumption of no cross-over effects and data following an approximate normal distribution, we will fit generalized linear mixed models (GLMMs) to the data examining the effects of group (PMS, iASD), condition (placebo, drug), time (baseline, week-12). Interactions on clinical and VEP measures will be checked for differential treatment effects, including subject level random

intercepts, to control for within subject correlations. Next, we will add baseline VEP gamma band activity, along with its interactions, to the models for clinical outcomes. In particular, a VEP by group by time interaction would suggest that the electrophysiological marker is predictive of differential treatment response. We will repeat these analyses with secondary electrophysiological markers and any derived composites. To examine whether electrophysiological markers track changes in clinical profiles, we will fit an additional GLMM with VEP values included as a time-varying rather than baseline covariate. If treatment effects become less significant it will suggest that rhGH is acting on clinical outcomes through the biomarker. Finally, we will directly correlate week-12 change scores for EEG and clinical measures. In case of major cross-over effects, we will base our primary analysis on phase 1 data only as a parallel group study. All tests will use a two-sided α of .05.

Power Analysis: Power is calculated for drug group differences in baseline to week 12 change scores in VEP gamma power since we are primarily interested in an overall treatment effect rather than a differential effect by group. These correspond to paired t-tests, taking advantage of the crossover design. With α at .05, we have 80% power to detect moderate to large effects ($d=.77$ within each group, $d=.53$ across groups), a reasonable expectation based on the potentially disease modifying effects of IGF-1 and our pilot study, which found a large effect ($d=1.05$) of IGF-1 in PMS on a different primary outcome (ABC-SW).

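### A treatment effect that becomes less significant once VEP is added does not show that rhGH acts through VEP; report a within-child indirect effect with a confidence interval instead

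*Combined protocol and SAP*

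**What the plan says.** All of this is in the combined protocol and SAP, mostly under Approach, Aim 3, Data Analysis.

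- Clinical and VEP outcomes are modelled with group, condition and time (baseline, week 12) and a random intercept per child. Baseline gamma activity is then added to the clinical models, and the step is repeated for secondary markers.
- To see whether "electrophysiological markers track changes in clinical profiles, we will fit an additional GLMM with VEP values included as a time-varying rather than baseline covariate".
- The reading rule follows directly: "If treatment effects become less significant it will suggest that rhGH is acting on clinical outcomes through the biomarker".
- A separate last step is listed: "Finally, we will directly correlate week-12 change scores for EEG and clinical measures". The rule does not depend on it.
- The rationale for Aim 3 expects that "the knowledge gained will provide evidence of targeted brain engagement with rhGH, a mechanistic pathway, and evidence of clinical efficacy".
- Outcome measures makes MSC at 30–36 Hz the primary electrophysiological outcome. P60-N75 amplitude is secondary.

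The documents give no indirect effect, no confidence interval for one, no threshold for *less significant* and no statement on confounding between VEP and outcome.

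**The concern.** The rule compares two p-values for the treatment effect, one without VEP in the model and one with it. Three things can raise the second p-value without any mediation.

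1. If the drug moves VEP, as the plan expects, VEP is collinear with treatment and the standard error of the treatment effect widens.
2. Raw time-varying VEP in a random-intercept model carries both between-child and within-child association. If children with lower VEP are also more affected, and the drug moves VEP, the treatment term can shrink although no child's outcome follows that child's VEP.
3. The plan expects some electrophysiological data to be lost (Potential pitfalls). It does not say that both models use the same visits, and a smaller data set can itself raise p.

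The mechanistic reading is at stake. This is the only criterion in Data Analysis for rhGH working through the biomarker. A wrong call could carry forward into how later trials select patients and markers.

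**Working it through.** **Plan's own figure.** Power Analysis states 80% power for d = .77 (n = 15) and d = .53 (n = 30), paired t-test, two-sided α = .05. The noncentral t distribution gives 79.2% and 80.1%, so these figures reproduce. They concern VEP gamma change. The plan gives no figure for the mediation rule.

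**Why p moves without mediation.** Take each child's drug-minus-placebo difference in change score. Without VEP, t = d√n = .53 × √30 = 2.90 (29 df, p ≈ .007). Now add the VEP difference as a regressor, with VEP d = .53 and no relation to the outcome. The estimate is unchanged on average, but its variance is multiplied by about

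1 + n·d²/(n − 1) = 1 + 30 × .2809/29 = 1.29.

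The standard error therefore grows by √1.29 = 1.14, and t falls to 2.90/1.136 = 2.56 (28 df, p ≈ .016). The drop is smaller in the four-visit mixed model, but its direction is the same.

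**Simulation inputs.**
- From the plan: 30 children (15 + 15), a 2×2 crossover, baseline and week 12 in each phase, random intercept, α = .05.
- Assumed: clinical d = .53 (the plan gives .53 only as the detectable gamma effect), VEP d = 0 or .53, unit visit noise, normal data, no dropout. A period term was included, which the plan's list of terms lacks; group interactions were left out.
- Quantity tracked: p of condition × time, without and with raw time-varying VEP (REML).

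**One run, 1,200 trials per setting, equal between- and within-child variance**

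| Setting | p rises | Estimate shrinks | Significant before | Significance lost (all trials) |
|---|---|---|---|---|
| No mediation, VEP d = 0 | 61.5% | 48.9% | 81.0% | 1.2% |
| No mediation, VEP d = .53 | 67.0% | 51.5% | 82.1% | 3.9% |
| 25% mediated | 99.2% | 99.2% | 79.2% | 23.7% |
| 50% mediated | 97.5% | 97.9% | 73.9% | 42.6% |

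Without mediation the estimate shrinks about half the time, as chance alone would give, yet p rises in about two-thirds of trials. Repeat runs with other variance ratios gave 62–67% and 97–99% for a rise in p.

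**Loss of significance.** Repeat runs gave 1–7% with no mediation, and about 25% and 46–48% at 25% and 50% mediation. The latter pair moves with the denominator and the variance assumptions. In the table, dividing by trials significant before adjustment gives .237/.792 = 30% and .426/.739 = 58%. The lowest runs gave 17–18% and 35–36% of all trials.

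**Between-child correlation, no mediation, VEP d = .53.** A rise in p occurs in roughly 85–97% of trials for r = .27 to .53. That overlaps the rate under true mediation.

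**Different visits.** If 10% of VEP visits are missing (assumed) and only the VEP model drops them, p rises in 74% of no-mediation trials, against 66% when both models use the same visits.

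**The case against.** **The headline rate uses the weakest reading.** Any rise in p, however small, counts towards the 62–67%. In one rerun the median fall in |t| was only .02–.08 without mediation, against .52 and .90 at 25% and 50% mediation. A reader might infer that two-thirds of null trials would yield a mechanistic claim. The documents do not support that, because an analyst who waited for significance to be lost would be wrong far less often. What stands is that the plan does not say which reading applies. The 97–99% also assumes that visit-to-visit VEP variation itself drives the outcome; if that variation is only measurement noise, one set of runs gave 66–90%.

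**The rule sits among other analyses.** The same paragraph tests drug effects on VEP and correlates change scores. Requiring a rise in p together with a significant change-score correlation cut false calls to 1–3%, although noise shared within a visit (correlation .2 or .4) brought them back to 18% or 60%. This is a fair point, but the plan does not require the results to be read jointly.

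**The marker.** A reader might infer that no marker is specified. The preceding sentences and Outcome measures make low gamma MSC the natural reading, so one clarifying phrase is enough.

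**Between-child confounding.** A reader might take the reported r = −.529 (n = 32) with the SAND as proof of the 85–97% scenario here. It is not. That coefficient is for P60-N75, the secondary marker, across groups. The treatment-related change is reported for the other marker: "There was a significant increase in low gamma MSC following IGF-1 relative to baseline". No MSC–SAND coefficient is given. The group term, and the iASD entry limit of "amplitudes within one standard deviation of the PMS mean", may also reduce any such correlation.

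**Conclusion.** The criterion is wrong as written and should be replaced. The argument of principle holds with confidence: a p-value comparison does not estimate an indirect effect, and p often rises when there is none. The sizes rest on assumed effects and variances. They are about 62–67% against 97–99% for any rise in p, and about 1–7% against roughly 25% and 46–48% for loss of significance. How much between-child correlation would add in this trial is unknown.

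The consequence is limited. This is a secondary analysis, worded as suggestive, within a feasibility aim. A reader might infer that the treatment comparison itself is compromised; it is not, and neither the primary test nor its power depends on this step.

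**What to change.** In Data Analysis:

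1. Delete the sentence that reads reduced significance as action through the biomarker.
2. State that the marker is low gamma MSC (30–36 Hz), with P60-N75 amplitude as secondary.
3. Split VEP into each child's mean and the visit-level deviation from it, and fit the models with and without VEP on the same visits.
4. Report the indirect effect (drug effect on VEP × within-child VEP–outcome slope) with a 95% CI from a bootstrap that resamples children. Label it exploratory.
5. Say *consistent with mediation* only if that CI excludes zero and the planned week-12 change-score correlation agrees in direction. Higher SAND scores mean more symptoms, so for a benefit a gain in MSC should go with a fall in SAND hyporeactivity.
6. State the assumption of no unmeasured within-child confounding, including noise shared within a visit, which can by itself make the CI exclude zero. In one set of no-mediation runs it did so in 28–41% of trials at a noise correlation of .2.

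A contrast pairing week-8 VEP with week-12 outcome can be added as a sensitivity analysis, since both are collected. It should not be a required condition: its simulated performance assumed the full drug effect by week 8, which nothing in the documents supports, and requiring it costs power.

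The cost is some plan wording and a short bootstrap, with no new data. The mechanistic claim also becomes harder to make with 30 children. In one set of runs the CI alone excluded zero in about 50–54% of trials at 25% mediation and 75–82% at 50%.

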Primary clinical outcome: SAND hyporeactivity subscale (Siper et al., 2017). Secondary and exploratory outcomes targeting ASD symptom domains: ABC-SW (Aman et al., 1985) and other measures employed in Aim 1 (Table 1) based on results from Aim 1. Clinical outcomes will be measured by an independent evaluator who is blind to side effects to prevent the risk of bias, and, within subjects, the same evaluator will complete assessments across all visits. Electrophysiological markers and clinical measures will be collected at baseline, weeks 4, 8, and 12 of each phase. Safety and tolerability will be measured after two weeks in each phase and then

every four weeks thereafter during monitoring visits and phone calls using an adapted semi-structured interview, the Safety and Monitoring Uniform Report Form (SMURF); extensive clinical

Table 1: Clinical Outcome Measures		
Domain	Instrument	Measurement modality
Social	Aberrant Behavior Checklist - Social Withdrawal Subscale	Caregiver report
Language /Communication	MacArthur-Bates Communication Development Inventory Vineland Adaptive Behavior subscales Mullen Scales for Early Learning subscales	Caregiver report Caregiver report Direct assessment
Repetitive Behavior	Repetitive Behavior Scales-Revised Aberrant Behavior Checklist - Motor Stereotypies Subscale Sensory Profile Sensory Assessment for Neurodevelopmental Disorders	Caregiver report Caregiver report Caregiver report Direct assessment
Adaptive Behavior	Vineland Adaptive Behavior Scales-3	Caregiver report

and laboratory

assessments will occur every four weeks during visits (see Protection of Human Subjects).

Language testing will include standardized measures reliant on caregiver report and objective standardized assessments. Specifically, caregivers will report on a child's expressive and receptive verbal and non-verbal communication repertoire on the MacArthur-Bates Communication Development Inventory (MCDI; Fenton et al., 2007), which is a valid assessment of young children's language (Charman et al., 2003; Luyster et al., 2007). Although not normed in children above 30 months of age, preliminary data collected on this measure suggest that raw scores on the MCDI are useful in capturing the range of language functioning in our minimally verbal and intellectually disabled sample. The MSEL and Vineland will provide standardized assessments of receptive and expressive language, by direct assessment and parent interview, respectively.

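### The primary analysis can switch to phase 1 only on the trial's own data, with no trigger outcome, formal test or threshold; .05 cannot be shown to hold, and the 80% power covers only the paired analysis

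*Combined protocol and SAP*

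**What the plan says.** All references are to the Combined protocol and SAP, Approach, Aim 3.

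- **Data Analysis, first step:** "First we will use graphical and numerical statistics to characterize treatment-, period- and cross-over effects". A crossover textbook is cited for this step.
- **Data Analysis, default:** "Under the assumption of no cross-over effects and data following an approximate normal distribution, we will fit generalized linear mixed models", with subject-level random intercepts.
- **Data Analysis, exception:** "In case of major cross-over effects, we will base our primary analysis on phase 1 data only as a parallel group study".
- **Data Analysis, error rate:** "All tests will use a two-sided α of .05".
- **Power Analysis:** 80% power for d=.77 within each group of 15 and d=.53 across all 30 children. "These correspond to paired t-tests, taking advantage of the crossover design".
- **Outcome measures:** there are two primary outcomes. "The primary electrophysiological outcome will be VEP gamma band activity as measured by MSC", and "Primary clinical outcome: SAND hyporeactivity subscale".
- **Potential pitfalls:** there is a four-week washout, and no significant carryover was seen in preliminary data. No figures are given.

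**The concern.** Which analysis is primary depends on what the trial's own data show, and the step from looking to deciding is unwritten. Three things are open: which outcome is inspected (VEP gamma MSC, SAND hyporeactivity, or each for itself), what statistic is used, and how large it must be. A reader of the results could not tell whether the default was left under a rule or after seeing which analysis was favourable.

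Two consequences follow. First, a preliminary check that shares data with the phase-1 comparison can select trials in which that comparison is already extreme by chance, so testing it at .05 afterwards need not give .05. Second, if the switch fires, the result rests on 15 against 15 children compared between subjects. The plan states no power for that comparison.

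**Working it through.** **Inputs from the plan.** 30 children (15 PMS, 15 iASD), two sequences, two-sided α=.05, paired d=.77 (n=15) and d=.53 (n=30), outcome = baseline to week 12 change.

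**Assumptions not in the plan.** 1:1 sequences (15 each), normal change scores, no dropout, the form and level of the carryover check, and ρ, the correlation between a child's two phase changes.

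**Choice of ρ.** With a random intercept only, every pair of visits has the same covariance c. The covariance of the two changes is then c − c − c + c = 0, so ρ=0. If correlation instead decays with time at .5 or .8 per 12 weeks (visits at weeks 0, 12, 16, 28), ρ is -.20 or -.09. The main range is therefore -.25 to 0. Positive values need further structure, such as child-specific trends, and serve only as a sensitivity range.

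**Step 1. The plan's own figure.** Power of a paired t-test is noncentral t with df = n−1 and noncentrality d√n.
- n=15, d=.77: 79.2%.
- n=30, d=.53: 80.1%.

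The stated 80% reproduces.

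**Step 2. Phase 1 alone, same raw effect.** The SD of the paired difference is the change-score SD times √(2(1−ρ)), so d(phase 1) = .53 × √(2(1−ρ)). Power is noncentral t with 28 df and noncentrality d√(15/2).

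| ρ | d in phase 1 | Power |
|---|---|---|
| -.25 | .84 | 60% |
| 0 | .75 | 51% |
| .25 (sensitivity) | .65 | 40% |
| .5 (sensitivity) | .53 | 29% |
| .8 (sensitivity) | .34 | 14% |

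Phase 1 reaches 80% only at d of about 1.06.

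**Step 3. Type I error of one possible switch.** This uses 200,000 simulated trials per setting with no drug effect and no carryover. The check compares each child's sum of the two phase changes between sequences. If it is significant, the phase-1 t-test is used; otherwise the crossover t-test is used. Both are at .05.

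| ρ | Overall, check at .05 / .10 | Phase-1 test given a trigger, .05 / .10 |
|---|---|---|
| -.25 | 6.0% / 6.5% | 25% / 19% |
| 0 | 6.4% / 6.9% | 32% / 24% |
| .25 (sensitivity) | 6.8% / 7.5% | 42% / 30% |
| .5 (sensitivity) | 7.3% / 8.1% | 52% / 36% |
| .8 (sensitivity) | 8.2% / 9.0% | 69% / 45% |

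A fixed crossover test gives about 5.0%. In the main range the conditional values run from 19% to 32%. Allowing two simulation standard errors (up to about one point), I quote them as about 18–33%. With the check at .01 the overall rate in the main range is 5.4–5.5%.

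**Step 4. Other checks, at .05 to .10.**
- Raw phase-2 baselines: 4.4–4.9% overall, no inflation.
- Change between the two baselines: 3.9–4.3% if all visits are equally correlated, 5.7–6.4% if correlation decays with time.

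So the same sentence in the plan is compatible with rates below and above .05.

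**Step 5. Power of the whole procedure.** With no carryover and the sum check, power is 77–80%, because the switch fires in only 1–10% of trials. In those trials power is about 49–56%.

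**The case against.** **There is a check.** The plan commits to looking at cross-over effects by graphs and numerical summaries. A reader might infer that nothing at all is specified; that would be wrong. What is missing is a decision rule. The textbook is cited for describing the effects, and the plan adopts no rule from it.

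**The general α statement could cover a carryover test.** This is possible, but no such test is named. On the sum check, a .05 level still gives 6.0–6.4% in the main range.

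**A switch is unlikely, and the trial is exploratory.** The washout and preliminary data do make a switch less likely, and the aim is framed as feasibility. This lowers the stakes without defining the rule. The Expected outcomes section also says that positive results would demonstrate efficacy in PMS and hopes for disease-modifying effects, so persistence after washout cannot be dismissed.

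**The fallback has a purpose.** This is the strongest point. If carryover is real, the crossover estimate is biased and phase 1 is not. Take a true effect of .50 SD and carryover of half to all of it (.25 to .50). Carryover present at phase-2 baseline but gone by week 12 moves the change-score estimate to .50 + .25/2 = .63 up to .50 + .50/2 = .75. Equal carryover at both times leaves it at .50. An estimate from week-12 values, with carryover lasting to week 12, falls to .50 − .25/2 = .38 down to .50 − .50/2 = .25. This stands as a real cost of fixing the crossover analysis, and is why phase 1 should be reported beside it.

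**The power statement is not wrong.** It is openly tied to paired t-tests and it reproduces. Fallback power is a gap rather than an error.

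**Conclusion.** The point holds: the choice of primary analysis is data-dependent, with no trigger outcome, formal test or threshold, and .05 cannot be shown to hold. If the check were the sum over phases at .05 to .10, overall type I error would be about 6–7%, and that of the phase-1 test given a trigger about 18–33%. Phase-1 power for the planned effect is about 51–60%, against 80% for the paired analysis. These sizes rest on 15 per sequence, normal change scores and ρ of -.25 to 0.

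Three stronger readings are not supported:
- *The trial's error rate is inflated to 7–9%, or its fallback power is only 14–40%.* Those figures need ρ of .25 to .8, which the plan's random-intercept model does not imply. Some checks cause no inflation at all.
- *A positive phase-1 result after a switch is probably false.* The 18–33% is a rejection rate when there is no effect. The chance that a positive result is false also depends on how likely a real effect is.
- *The trial as a whole is underpowered because of the switch.* Without carryover, the whole procedure under the sum check keeps 77–80%.

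This should be fixed, and it can be settled before unblinding.

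**What to change.** Rewrite the Data Analysis paragraph as follows:

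1. Remove the data-dependent switch. Make the two-period crossover analysis primary for both VEP gamma MSC and SAND hyporeactivity, whatever the inspection of cross-over effects shows.
2. Report the phase-1-only comparison for both outcomes as a pre-specified sensitivity analysis, with its confidence interval and its power over a stated range of ρ.
3. Report the difference between sequences in phase-2 baselines descriptively.
4. State that real carryover may bias the crossover estimate in either direction, and that it will be read beside the phase-1 result.

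The cost is one paragraph and no new data, since both measures are already collected at the baseline of each phase. The price is the possible bias in item 4.

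If the sponsor prefers to keep a switch, the alternative is to fix the outcome, check and threshold before unblinding and to state the simulated type I error and power of that rule. This cures the ambiguity, but such checks are weak at this size. At p<.05 the sum check (ρ=0) detects carryover of half the drug effect in 11% of trials and of the whole effect in 29%. A check on raw phase-2 baselines detects 10–17% and 24–51%.
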